### **Data Analysis**

Access to Data will be limited to the P.I., research coordinator, and research nurse. Approval from the IRB to allow access to data will be sought via an IRB amendment application if any additional research personnel are added to the study.

Confidentiality of patients will be protected by assigning numbers to patients and avoiding use of PHI. Results of the study will be reported in aggregate and anonymously

Statistical analyses will be conducted by the section of Biostatistics in the Quantitative Health Sciences department at the Cleveland Clinic using the methods described below:

### **Statistical Methods**

Patient and disease characteristics will be summarized using means, standard deviations, medians and other percentiles of interest for continuous measures and frequencies and percentages for categorical factors. Changes in scoring tool measures from baseline to six months will be calculated and compared using paired t-tests. If necessary, transformations of the data will be performed prior to analysis to meet distributional assumptions. If proper transformations cannot be found, then nonparametric Wilcoxon

signed rank tests will be performed. To assess trends scores over time, linear mixed effect models will be fit and estimates of the average change per month will be calculated. Analysis will be performed using SAS software (The SAS Institute; Cary, NC). A significance level of 0.05 will be assumed for all tests.

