## **Research Procedures**

- 1) Upon enrollment patients will undergo a thorough history (including assessing time of diagnosis), review of systems, and a complete physical examination.
- 2) A detailed examination of the skin and mucous membranes will be performed, noting for presence/absence of the following: scalp erythema and atrophy, heliotrope rash, typical erythema and atrophy of sun-exposed areas on the neck, upper chest and upper back (shawl sign), erythema +/- scaling of the elbows and/or knees (Gottron's sign), gottron's papules, periungual erythema, ragged cuticles, proximal nailfold capillary loops, palmar scaling and hyperkeratosis (mechanic's hands), a rash involving the hips (holster sign), oral ulcerations, cutaneous ulcerations, purpura.
- 3) Objective cutaneous dermatomyositis scoring by the primary investigator using the **modified Cutaneous Dermatomyositis Disease Area and Severity Index** (CDASI) score and **Abbreviated Cutaneous Assessment Tool** (aCAT) will be performed at each visit ([8-13](#)).
- 4) Objective general cutaneous disease scoring by the primary investigator using the **Physician Global Activity** for (a) **overall skin** (b) **skin activity** (c) **skin damage** will be performed at each visit (each assessed using both VAS-0-10 visual analog scale and Likert scale- 0-4 for each) ([9](#)).
- 5) Objective scoring tools to be completed by the patient at each visit will include: **Patient Global Assessment (Skin) Score** (0-10 visual analog scale), **Patient Global (Itch) Score** (0-10 visual analog scale), and the **Dermatology Life Quality Index** (validated quality of life assessment) ([8-12](#)).
- 6) Photographs of all cutaneous lesions will be performed at baseline and at each follow-up visit.
- 7) Evaluation for current presence of myositis will be performed using the **Manual Muscle Testing 8 (MMT-8)** scoring tool by the primary investigator, as well as with serologic studies below ([11, 12](#)).
- 8) Completion of the **Myositis Disease Activity Assessment Tool** (MDAAT) by the primary investigator to assess disease activity of extramuscular organ systems ([12](#)).
- 9) Serologic studies at baseline will include an AM cortisol level, CBC w/ diff, CMP, CK, aldolase, LDH, comprehensive myositis panel (ARUP labs), C3, C4, and HbA1c. The above serologic studies (except for the comprehensive myositis panel) will be repeated at the final visit.

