10) Patients may continue their current immunosuppressive treatment regimens at the time of starting H.P. Acthar. If it is felt that patients should taper off of medications they will require a washout period:

- corticosteroids- 2 weeks
- methotrexate/azathioprine/mycophenolate/cyclosporine/sirolimus- 4 weeks
- adalimumab/infliximab/IVIG/chlorambucil/cyclophosphamide- 8 weeks
- rituximab- 6 months.

They will be instructed to continue topical medications, moisturizers, and sunscreen based on their current practice, which will be recorded at baseline and during subsequent visits.

11) All patients will receive 80 U (1 mL) of H.P. Acthar gel via subcutaneous injection twice weekly for 24 weeks (approximately 6 months).

12) Patients will require **follow-up visits in person at 1mo (+/- 5 days), 3mo (+/- 5 days), and 6mo (+/- 5 days)** after initiation of the H.P. Acthar, at which time examinations and clinical scoring tool assessments will be repeated.

13) If corticosteroids are continued in patients receiving H.P. Acthar gel they will be tapered at the primary investigator's discretion based on clinical evaluation at follow-up appointments.

14) H.P. Acthar will be discontinued in any given patient at the primary investigator's discretion if deemed necessary for the patient's overall health and well-being at any point during the study.

Serologic Studies	Baseline	6mo
CBC w/ diff	X	X
CMP	X	X
AM cortisol level	X	X
Creatine Kinase	X	X
Aldolase	X	X
LDH	X	X
C3	X	X
C4	X	X
HbA1c	X	X
Comprehensive myositis panel (ARUP labs)	X	

Length of above tests is that of a typical phlebotomy blood draw.

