### **Study End Points**

#### **1. Primary end-points:**

Statistically significant improvement in cutaneous manifestations of dermatomyositis based on changes in **modified CDASI** score, **CAT** score, and **Physician's Global Assessment (overall, activity, damage)** scores at end of study vs. baseline.

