## **Sample Size Considerations**

The primary assessment tool will be the CDASI. Scores for the modified CDASI range from 0 to 100 for activity, 0 to 32 for damage, and 0 to 132 for the total score. In the paper by Yassaee (2010), investigators found a mean (SD) activity score of 17.83 (10.14), a mean (SD) damage score of 2.27 (2.73), and a mean (SD) total score of 20.10 (10.25). Given the apparent skewed distributions for these scores, a log-normal distribution for the scores was assumed. In these distributions, a coefficient of variation (CV = SD/Mean) of 0.6 appears appropriate for activity and total scores, while a CV of 1.25 was assumed for comparisons of total score. The required sample size for each scale to achieve 80% power to detect 25%, 50%, and 75% decreases in CDASI scores, based on the assumptions above, and assuming use of two-sided paired t-tests on log-transformed values. These calculations further assume that a small positive correlation ( $r=0.25$ ) between baseline and 6-month scores within person, and use of a 0.05 significance level. Note that since Activity and Total CDASI scores assume the same CV, sample size requirements are identical. Under these assumptions, 10 patients are needed to detect a 50% decrease in the mean CDASI activity score or CDASI total score with 80% power. This sample size would allow adequate power to detect decreases of at least 70% in the mean damage score. Eight patients would be required to detect a 75% decrease in the mean damage score.

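### The 6-month test uses only patients with a 6-month score; prespecify a 6-month contrast from the already planned mixed model so that the 1- and 3-month scores count

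*Combined protocol and SAP*

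**What the plan says.** - **Test.** Statistical Methods: "Changes in scoring tool measures from baseline to six months will be calculated and compared using paired t-tests". If the data cannot be made suitable: "If proper transformations cannot be found, then nonparametric Wilcoxon" signed rank tests follow. Both need a baseline and a 6-month score.
- **Mixed models.** The same section plans linear mixed models for trends, from which "estimates of the average change per month will be calculated". No 6-month contrast is named.
- **Visits.** Research Procedures, item 12, requires "follow-up visits in person at 1mo (+/- 5 days), 3mo (+/- 5 days), and 6mo (+/- 5 days" each), and the schedule of clinical assessments repeats every scoring tool at all of them. Physician's Global scores are "each assessed using both VAS-0-10 visual analog scale and Likert scale- 0-4 for each".
- **Endpoint.** The primary end-points compare "scores at end of study vs. baseline".
- **Stopping.** Item 14 lets the investigator stop the drug for the patient's "overall health and well-being at any point during the study". It does not say whether scoring continues afterwards.
- **Not stated.** There is no analysis set, no rule for a missing 6-month score and no allowance for dropout.

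**The concern.** A paired test without a missing-data rule becomes a completers' analysis. With about 10-15 patients, one or two missing 6-month scores are a large share of the data. If those patients were doing badly at month 3, the remaining patients look better than the whole group. A single-arm, open-label study has no control group in which the same distortion would show. Success is defined as statistically significant improvement, so false improvement is the error that matters. Scores already collected at month 3 carry information about the missing values, and the planned test ignores them.

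**Working it through.** **1. The plan's own figure.** Inputs from Sample Size Considerations: CV 0.6, r = 0.25, log scale, two-sided 0.05, 50% decrease.
- Log variance = ln(1 + 0.6²) = 0.3075, so σ = 0.5545.
- SD of log change = √(2 × 0.3075 × 0.75) = 0.679.
- Standardised effect = ln 2 / 0.679 = 1.02.
- Noncentral t power is 81.9% with 10 pairs. The stated N of 10 reproduces.
- Power is 76.5% with 9 pairs and 69.8% with 8.

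**2. Shift in the completers' mean if the worst month-3 changes are lost.** Let D3 and D6 be the log changes from baseline to months 3 and 6, and r03, r06, r36 the correlations. Only r06 = 0.25 is in the documents; the others are assumptions. With k of 10 lost,

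shift = −c_k × σ(1 − r03 − r06 + r36) / √(2(1 − r03)).

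The two largest expected normal order statistics for n = 10 are 1.539 and 1.001, so c₁ = 1.539/9 = 0.171 and c₂ = (1.539 + 1.001)/8 = 0.3175.

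- **All correlations 0.25.** The factor is 0.5545 × 0.75/√1.5 = 0.340. One lost: shift −0.058, an apparent decrease of 5.6% with no true effect. Two lost: −0.108, or 10.2%. A true 50% decrease reads as 1 − 0.5e^(−0.058) = 52.8%, or 55.1% with two lost.
- **Range over r03 0.25-0.6 and r36 0.25-0.8.** The factor runs from 0.5545 × 0.40/√0.8 = 0.248 to 0.5545 × 0.95/√0.8 = 0.589. Apparent decrease is about 4-10% (1 lost) or 8-17% (2 lost). A true 50% decrease reads as 52-55% or 54-59%.

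**3. False improvement with the paired t-test (simulated, no true effect, nominal 2.5%).**

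| Loss pattern | 1 lost | 2 lost |
|---|---|---|
| Unrelated to response, 10 enrolled | about 2.5% | about 2.5% |
| Random among the worse half at month 3, 10 enrolled | 3.0-3.6% | 3.6-5.5% |
| Worst at month 3, 10 enrolled, all correlations 0.25 | about 4.4% | about 6.5% |
| Worst at month 3, 10 enrolled, all assumed correlations | 3.9-7.3% | 5.0-13.8% |
| Worst at month 3, 15 enrolled, all assumed correlations | 3.6-6.9% | 4.9-13.0% |

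For the Wilcoxon fallback with 10 enrolled and the worst lost, the rates are 3.0-5.9% and 4.0-11.7% against a nominal 2.0%.

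**4. The alternative.** With the worst lost and 10 enrolled, the month-6 contrast from a model with categorical visit, unstructured covariance and Kenward-Roger degrees of freedom shows an apparent change under 1%. False improvement is 2.5-3.3% (1 lost) and 3.9-5.2% (2 lost). These two rates rest on one set of simulations (4,000 trials per case, four assumed correlation matrices). A separate check by generalised least squares with known correlation, 2 of 10 lost and a true 50% decrease, gave 50% from the model and 55-56% from the paired test.

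The planned monthly slope is not a substitute. Multiplied by 6, and with a random intercept assumed because the plan names no random effects, it gave 2.5-12.2% and 2.9-16.6% false improvement in the same setting.

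**5. Damage scores.** The plan cites "a mean (SD) damage score of 2.27 (2.73"). Under a log-normal with those values, 13% of baseline scores fall below 0.5, and 35% after a 50% decrease. Zeros are therefore likely and a log-scale model is unsuitable. For activity the corresponding figures are at most 0.2% and 1.1%.

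**The case against.** The strongest reply is that nothing here has to go wrong, and most of it stands.

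- **No evidence of response-related loss.** The documents do not say that patients will be dropped from analysis; this follows from the choice of test and the lack of a rule. Item 14 concerns health and well-being, not skin response, and visits are timed from the start of treatment, with no condition that treatment continues. A reader might infer that the trial will be biased. The documents do not support that.
- **The upper figures are extremes.** Rates near 13.8% need exactly the two worst month-3 responders lost, no drug effect and an assumed correlation of 0.8 between months 3 and 6. At the planned 50% effect, even this loss does not change the conclusion.
- **The endpoint time is not really open.** A reader might infer that the end of study is undefined. Statistical Methods fixes six months, and neither item 12 nor the schedule lists a later visit.
- **The model does not rescue power.** A reader might expect it to recover the power lost with missing pairs. Under random loss its standard error is only about 3-7% smaller in most assumed cases.
- **Imputing no change is not shown to be wrong.** It leaves most of the bias when there is no true effect. At a true 50% decrease with the worst two lost it reads 46-51%, against 54-59% for the paired test. No rule against it is justified.

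What remains is that the plan already fits mixed models to these scores, and a visit-based 6-month contrast reduces a plausible bias at almost no cost.

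**Conclusion.** The point holds as a conditional one and should be fixed. The 6-month test ignores 1- and 3-month scores that could reduce bias when loss follows observed response. With 10 enrolled, no true effect, the worst month-3 responders lost and r = 0.25 throughout, false improvement is about 4.4% (1 lost) or 6.5% (2 lost) against 2.5%. With 2 lost it is about 3.6-5.5% if loss is random in the worse half, and 5.0-13.8% across the assumed correlations if the worst are lost. If loss is unrelated to response, there is no bias. The loss pattern, the number lost and every correlation other than baseline to month 6 are assumptions, so confidence in the size is moderate.

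**What to change.** For the continuous primary scores (CDASI activity and total on the log scale, CAT, Physician's Global VAS), prespecify the month-6-minus-baseline contrast from the planned mixed model as the main 6-month estimate:
- visit as a categorical factor (baseline, 1, 3, 6 months);
- all treated patients with a baseline score;
- unstructured covariance and Kenward-Roger degrees of freedom;
- if the four-visit fit does not converge, use baseline, 3 and 6 months; if that also fails, use the paired test.

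Report the paired t-test or Wilcoxon beside it. Keep the paired test or Wilcoxon for the 0-4 Likert scales and for damage scores with many zeros. State how many patients lack a 6-month score. As a wording tidy-up, name the 6-month visit in the primary end-points.

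A sensitivity analysis that gives patients without a 6-month score the worst change seen in any completer is optional. With 2 of 10 lost at random it has about 51% power for a true 50% decrease, against about 70% for the paired test.

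**Cost.** No new visits or data. With no missing scores the contrast equals the paired t-test (same estimate and standard error, 9 degrees of freedom with 10 patients). The downsides are:
- The four-visit fit has 10 covariance parameters for 10-15 patients. It failed to converge in 0.5-0.7% of simulated trials with 2 of 10 lost; the three-visit fit (6 parameters) failed in 0.1% or less.
- False improvement is still about 4-5% with the worst 2 of 10 lost.
- The model does not correct loss driven by unseen month-6 outcomes.

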## **Sample Size Considerations**

The primary assessment tool will be the CDASI. Scores for the modified CDASI range from 0 to 100 for activity, 0 to 32 for damage, and 0 to 132 for the total score. In the paper by Yassaee (2010), investigators found a mean (SD) activity score of 17.83 (10.14), a mean (SD) damage score of 2.27 (2.73), and a mean (SD) total score of 20.10 (10.25). Given the apparent skewed distributions for these scores, a log-normal distribution for the scores was assumed. In these distributions, a coefficient of variation (CV = SD/Mean) of 0.6 appears appropriate for activity and total scores, while a CV of 1.25 was assumed for comparisons of total score. The required sample size for each scale to achieve 80% power to detect 25%, 50%, and 75% decreases in CDASI scores, based on the assumptions above, and assuming use of two-sided paired t-tests on log-transformed values. These calculations further assume that a small positive correlation ( $r=0.25$ ) between baseline and 6-month scores within person, and use of a 0.05 significance level. Note that since Activity and Total CDASI scores assume the same CV, sample size requirements are identical. Under these assumptions, 10 patients are needed to detect a 50% decrease in the mean CDASI activity score or CDASI total score with 80% power. This sample size would allow adequate power to detect decreases of at least 70% in the mean damage score. Eight patients would be required to detect a 75% decrease in the mean damage score.

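### Damage-score power is calculated for a plain-log paired t-test that cannot take zeros and is not the default analysis; power for the zero-tolerant tests the plan names was not calculated and is probably lower

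*Combined protocol and SAP*

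**What the plan says.** Sample Size Considerations describes the modified CDASI as the primary assessment tool. It gives the subscale range as "0 to 32 for damage" and takes a reference damage mean (SD) of 2.27 (2.73) from a cited paper. It assumes log-normal scores and a within-person correlation of 0.25, and works out power "assuming use of two-sided paired t-tests on log-transformed values". For 10 patients it concludes: "This sample size would allow adequate power to detect decreases of at least 70% in the mean damage score". It then adds: "Eight patients would be required to detect a 75% decrease in the mean damage score". No added constant and no rule for zero scores is given.

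Statistical Methods sets a different default: "Changes in scoring tool measures from baseline to six months will be calculated and compared using paired t-tests". Transformation is conditional: "If necessary, transformations of the data will be performed prior to analysis to meet distributional assumptions". The Wilcoxon signed rank test follows if no suitable transformation is found.

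The Sample section plans about 10-15 patients. It cites power for a 75% fall in damage as part of the reason, and says this does not depend on the baseline score.

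**The concern.** The powered test and the planned test are not the same. A plain log cannot be taken of a zero. On a scale that starts at 0, a 70% fall from 2.27 leaves a mean of 2.27 × 0.30 = 0.68, and a 75% fall leaves 2.27 × 0.25 = 0.57. Zeros at 6 months are then likely, and the analysis behind the power figure could not be run as described.

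Two things are at stake. A non-significant damage result could be read as coming from a test with 80% power when it had less. And the tests that Statistical Methods allows differ enough in power that choosing among them after seeing the data would matter.

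**Working it through.** **Inputs from Sample Size Considerations.** CV 1.25, r = 0.25, two-sided alpha 0.05, target power 80%, reference damage mean 2.27. The text attaches the CV to the wrong scale ("while a CV of 1.25 was assumed for comparisons of total score"). The reference figures show that damage is meant: 2.73/2.27 = 1.20 for damage, against 10.25/20.10 = 0.51 for total.

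**Step 1: reproduce the plan's figures (plain logs, noncentral t).**
- Log-scale variance: ln(1 + 1.25²) = 0.941.
- SD of the log difference: √(2 × 0.941 × 0.75) = 1.188.
- 70% fall, n = 10: effect |ln 0.30|/1.188 = 1.013; noncentrality 1.013 × √10 = 3.20; power 81.3%.
- 75% fall, n = 8: effect |ln 0.25|/1.188 = 1.167; noncentrality 1.167 × √8 = 3.30; power 80.7%.
- Activity and total, CV 0.6, 50% fall, n = 10: power 81.9%.

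All the stated figures reproduce.

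**Step 2: same continuous model, default test.** A raw paired t-test on these log-normal scores does not depend on the baseline mean, because rescaling the scores leaves the t statistic unchanged. Simulated power is about 54% (n = 10, 70% fall) and 50% (n = 8, 75% fall). It passes 80% at n = 17 and n = 14 respectively. This step assumes nothing about zeros or whole-number scoring.

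**Step 3: whole-number scores near the reference mean.** Assumptions not in the documents: scores are log-normal values rounded to the nearest integer, and this trial's baseline mean is 2.27. CV and r are as in the plan. Zeros are then 14% at baseline and, at 6 months, 57% (70% fall) or 64% (75% fall).

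| Test | n = 10, 70% fall | n = 8, 75% fall |
|---|---|---|
| log(score+1), paired t | 73% | 71-72% |
| log(score+0.5), paired t | 74% | 73% |
| square root, paired t | 73% | 71% |
| Wilcoxon signed rank | 59% | 49% |
| raw paired t | 55% | 52% |

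With log(score+1), power for a 70% fall reaches 82% at n = 12. For a 75% fall with n = 10 it is 83%, against about 65% for the raw t-test. Not all the loss comes from zeros: on continuous scores log(score+1) already gives 76% and 75%, because the offset itself costs power.

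**Step 4: sensitivity, same two combinations.**

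| Change from step 3 | log(score+1) | raw paired t |
|---|---|---|
| baseline mean 5 | 78% and 76% | 55% and 50% |
| baseline mean 8 | 79% and 78% | 59% and 53% |
| baseline mean 10 | 80% and 79% | 63% and 57% |
| r = 0.5, mean 2.27 | 85% and 83% | 66% and 62% |

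If scores behave as overdispersed counts with mean 2.27, log(score+1) gives about 41-47% and 38-44%, depending on the count model. For a 75% fall it gives 53-56% at n = 10 and 71-77% at n = 15.

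**Step 5: activity and total.** At means of 17.83 and 20.10 with CV 0.6, rounding produces virtually no zeros. log(score+1) keeps 82% at n = 10 for a 50% fall. A raw t-test would give 73% there; that reflects the choice of test, not zeros.

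**The case against.** Three stronger readings are tempting, and the documents do not support them.

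- *The plan names no test that can handle zeros.* It does. The raw paired t-test and Wilcoxon both accept zero scores (Wilcoxon drops only zero differences). What is missing is a zero rule for the log analysis, and power for the tests that are named.
- *The power arithmetic is wrong.* It is right under assumptions that the section discloses.
- *Pairs with a zero would be discarded, so power collapses.* Nothing in the plan prescribes discarding them.

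The best case for the plan goes further. The reference mean comes from a cited paper, not from this trial's refractory patients, whose baseline damage could be higher. Neither whole-number scoring nor the share of zeros is documented. The correlation of 0.25 is described as small, and a higher one helps. The planned sample is 10-15, so 8 is never the intended number, and the Sample section's own target (75% fall, at least 10 patients) keeps about 83% with log(score+1) in the rounding model. Since the sample size section already notes skewness, the analyst would probably transform rather than use raw changes.

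Most of this stands, and it limits the size of the point. It does not remove it. The raw t-test shortfall in step 2 needs none of the disputed assumptions, and the raw test stays below 80% at r = 0.5 and at every baseline mean tried. The likely switch to a transformation is not written down, nor is the transformation itself.

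**Conclusion.** The point holds in a limited form. The damage power figures are correct for a test that is not the named default and cannot be run on zero scores. On the plan's own continuous model the default raw t-test has about 54% and 50% power at the two stated combinations, not 80%. A zero-tolerant log test recovers most of the gap, to about 73% and 71-72%, if scores are whole numbers, the baseline mean is near 2.27 and r is 0.25. That smaller shortfall is conditional: it nearly vanishes at a baseline mean of about 10, reverses at r = 0.5, and is much larger if scores behave as counts.

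The statement that baseline level does not matter is true in the log-normal model, but not for damage scores near the floor. A reader might infer that the trial is too small; the documents do not show that. The figure of 10 rests on activity and total, which zeros do not affect. The stated damage power should be corrected because it is used to justify the sample and the permitted tests differ by about 18 points (73% against 55% at n = 10, 70% fall).

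**What to change.** - **Statistical Methods:** before data are seen, name one zero-tolerant test for damage, for example a two-sided paired t-test on log(score+1). log(score+0.5) performs about equally well; what matters is fixing one.
- **Sample Size Considerations:** restate damage power for that test with its assumptions (rounded log-normal, baseline mean 2.27, CV 1.25, r = 0.25): about 73% for a 70% fall with 10 evaluable patients, about 82% with 12, and about 83% for a 75% fall with 10. Show the sensitivity to r, baseline mean and count-type scores. Limit the sentence on eight patients to positive, continuous scores analysed on plain logs.
- **Sample:** make the damage claim conditional on the named test, those assumptions and at least 10 evaluable patients. Limit the statement that baseline does not matter to activity and total.
- **Clerical:** attach the CV of 1.25 to the damage score, not the total score. No stated figure changes.

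The cost is edits to three sections and a short simulation check by the trial statistician. No extra patients are needed. The downside is that the stated damage power becomes less favourable and carries explicit conditions.
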